### Potential Risks:

Per the Glucophage (metformin) package insert, metformin does not cause hypoglycemia in individuals with diabetes mellitus or normal subjects except in certain circumstances excluded by the study's exclusion criteria.

Metformin does have a warning for the risk of lactic acidosis. Per the insert:

The reported incidence of lactic acidosis in patients receiving metformin hydrochloride is very low (approximately 0.03 cases/1000 patientyears, with approximately 0.015 fatal cases/1000 patientyears). In more than 20,000 patient-years exposure to metformin in clinical trials, there were no reports of lactic acidosis. Reported cases have occurred primarily in diabetic patients with significant renal insufficiency, including both intrinsic renal disease and renal hypo perfusion, often in the setting of multiple concomitant medical/surgical problems and multiple concomitant medications.

In a more recent review of pooled data from 347 trials and cohort studies an estimated risk of 4.3 cases of lactic acidosis in 100,000 patient years was calculated and this risk was equivalent with other antihyperglycemic agents. The ultimate conclusion of this investigation was "There is no evidence to date that metformin therapy is associated with an increased risk of lactic acidosis or with increased levels of lactate compared with other antihyperglycemic treatments if the drugs are prescribed under study conditions, taking into account contraindications". 26

Other known adverse reactions to metformin therapy include gastrointestinal side effects which include flatulence, diarrhea, nausea and vomiting, and abdominal discomfort. These symptoms are dose dependent and can be relieved by dose reduction. Approximately 50% of all patients can tolerate a maximal dose of metformin but a small minority of around 5% cannot tolerate any dose of metformin.

## Potential Benefits:

The potential benefits to patients who agree to enroll in this study include the potential benefits of metformin therapy and the benefits of more frequent follow up. In addition the previously discussed evidence to show weight loss, metformin therapy has been demonstrated to have several potential beneficial effects including a decrease in progression from prediabetes to diabetes and improved cancer mortality compared to patients taking other diabetic therapies and non-diabetic individuals, 

#### **Statistics:**

We expect a 30% recurrence of AF after patients undergo ablation. After ablation, we expect the recurrence of AF to be 30% less in the intervention group of patients on metformin than the control group.

Using an 80% power at a 95% confidence interval, the sample size of the control group (ablation only) and the intervention group (ablation plus metformin) will be 400 each for a two tailed study, accounting for up to a 3% attrition rate in each group. The total sample size of this study will be 800. It is estimated to take five years to accrue subjects.

Statistical methods employed to analyze outcomes will be a Pearson's  $X^2$  test for categorical variables. Analysis of Variance will be used for continuous variables. All tests are two-sided and P < .05 will be used to indicate a statistically significant difference.

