#### **Trial Design:**

The proposed study will be a randomized control trial comparing metformin therapy to a control group in patients with a BMI  $\geq$ 27 and atrial fibrillation who have elected to undergo a rhythm control strategy with ablation. Upstream therapy with Metformin will be used in a randomized fashion. The only variation to the standard of care will be the addition of Metformin therapy and additional blood draws for safety monitoring and EKGs for measuring outcomes in both the intervention and control groups.

Patients meeting the below inclusion and exclusion criteria who provide informed consent will be randomized to control versus metformin therapy six weeks prior to rhythm control.

At baseline all study patients will be assessed for:

Age, Gender, Weight, BMI, Tobacco Use, Hypertension, Hemoglobin A1c, Hyperlipidemia, serum CRP, glomerular filtration rate estimating equation (eGFR), B12, liver function tests (AST, ALT, ALP, bilirubin, albumin, INR), lactic acid, History of Coronary Artery Disease by MI, PCI, or CABG, History of Valvular Disease, History of Obstructive Sleep Apnea, Type of AF and duration, Number of Antiarrhythmic Medications (not including beta-blockers or calcium channel blockers).

In addition, patients will fill out a survey to determine their Atrial Fibrillation Severity Score (AFSS) - a validated tool to assess the symptomatic burden of AF - and will receive education on dietary changes and exercise

Metformin will be initiated at 500 mg daily and increased as tolerated to 2000 mg daily over a three week period. Subjects will be instructed to hold Metformin on the day of any procedure or study requiring the administration of intravenous contrast and to resume 48 hours after the contrast administration and reinstituted only after renal function has been reevaluated and found to be at the patient's baseline. All patients will receive information on dietary changes to promote weight loss and will be encouraged to increase exercise activities. Patients will discontinue treatment at any time they are found to meet the baseline exclusion criteria for the study.

The initiation of the drug and the dosage increases will be overseen by a designee (mid-level cardiology practitioner) who will be responsible for stopping dosage increases if side effects occur. Six weeks after the initiation of drug the patient will undergo ablation with the intent of achieving rhythm control.

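### The primary chi-square is valid and adequately powered, but AF type, AF duration and BMI are collected at baseline and go unused; prespecified adjustment could add about 0 to 6 points of power.

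*Combined protocol and SAP*

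**What the plan says.** The Statistics section is the whole analysis plan: "Statistical methods employed to analyze outcomes will be a Pearson's" chi-square for categorical variables, analysis of variance for continuous ones, and "All tests are two-sided and P < .05 will be used to indicate a statistically significant difference". It names no covariate, regression model or stratified test, not even as a sensitivity analysis. Under Outcomes and Assessment of Efficacy the primary outcome is maintenance of sinus rhythm by intention to treat. That is categorical, so its planned test is the unadjusted chi-square.

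The baseline list in Trial Design includes BMI and "Type of AF and duration, Number of Antiarrhythmic Medications", and the list in Treatment of Subjects repeats these items. Method of Assigning Subject Identification allocates the arm through a randomly assigned subject number and mentions no stratification factor.

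The sample-size inputs are also in the Statistics section. The control rate is given as "We expect a 30% recurrence of AF after patients undergo ablation". For the size of the effect, the plan states that "we expect the recurrence of AF to be 30% less in the intervention group of patients on metformin than the control group". Power is set at 80% with 95% confidence. The two groups "will be 400 each for a two tailed study", and losses to follow-up are covered by the phrase "accounting for up to a 3% attrition rate in each group".

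**The concern.** When baseline variables predict a binary outcome, an analysis that adjusts for them is more precise at the same sample size. It also removes from the estimate the part of the arm difference that comes from chance imbalance in those variables. Here they are already to be collected in all 800 patients, over an accrual period put at five years, and neither the design nor the analysis uses them. If no model is fixed in advance, any later adjustment will be post hoc and open to challenge. What is at stake is some power and precision for the primary comparison, not its validity.

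**Working it through.** **1. Inputs.** From the Statistics section: control recurrence 0.30; metformin recurrence 0.30 × (1 − 0.30) = 0.21, reading the 30% as relative (an absolute reduction would give zero recurrence); difference 0.09; two-sided alpha 0.05; power 80%; 400 per arm; 3% attrition, leaving 400 × 0.97 = 388 per arm. Not in the documents, and therefore assumed: the prevalence of each AF type and how strongly any covariate predicts recurrence.

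**2. The plan's own figure.** With mean rate 0.255:

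n = [1.960 × √(2 × 0.255 × 0.745) + 0.842 × √(0.30 × 0.70 + 0.21 × 0.79)]² / 0.09² = 367 per arm.

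With continuity correction: n = (367/4) × [1 + √(1 + 4/(367 × 0.09))]² = 389. Allowing for attrition, 389/0.97 = 401.03, or 402. The stated 400 is reproduced. Without the correction the figure would be 367/0.97, or 379.

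**3. Power of the planned test at 388 per arm.** The standard error is √(2 × 0.255 × 0.745/388) = 0.0313 under the null and √((0.2100 + 0.1659)/388) = 0.0311 under the alternative.

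Power = Φ[(0.09 − 1.960 × 0.0313)/0.0311] = 82.1%.

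**4. Power with adjustment for AF type.** Assume two AF types, half the patients in each, and the same 30% relative reduction in both. Stratum rates are chosen so that the overall rates stay at 30% and 21%. The adjusted risk difference has SE = √((V0 + V1)/388), where V0 and V1 are the within-type averages of p(1 − p) in each arm. Power = Φ(0.09/SE − 1.960).

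Example, 15%/45% control recurrence by type:
- V0 = (0.1275 + 0.2475)/2 = 0.1875
- V1 (10.5%/31.5%) = (0.0940 + 0.2158)/2 = 0.1549
- SE = 0.0297; power = Φ(1.07) = 85.8%

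| Control recurrence by type (assumed) | Adjusted SE | Adjusted power, formula | Simulated power, unadjusted v adjusted |
|---|---|---|---|
| 30%/30% (not prognostic) | 0.0311 | 82.4% | 82.4% v 82.5% |
| 25%/35% | 0.0310 | 82.8% | 82.1% v 82.7% |
| 20%/40% | 0.0305 | 83.9% | 82.5% v 83.9% |
| 15%/45% | 0.0297 | 85.8% | 82.5% v 85.6% |
| 10%/50% | 0.0286 | 88.3% | 82.1% v 87.7% |

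The simulated gains are therefore about 0, 0.6, 1.4, 3.1 and 5.6 points. Type I error stays near 5% throughout.

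**5. A model of the recommended kind.** A separate simulation (6,000 trials per setting, simulation error about 0.5 points) used three baseline covariates, logistic regression and the standardised risk difference. Prognostic strength is given as the AUC of the covariates combined. Unadjusted v standardised power:
- AUC 0.50: 82.5% v 82.5%
- AUC 0.58: 82.8% v 83.8%
- AUC 0.64: 81.6% v 83.6%
- AUC 0.69: 82.5% v 85.6%
- AUC 0.74: 82.5% v 88.6%

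Null rejection was 4.9% to 5.2% for all methods.

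**6. Chance imbalance.** Under simple randomisation, the arm difference in a factor with 50% prevalence (assumed) has SD √(2 × 0.25/388) = 0.0359, so its 95% limit is 1.96 × 0.0359 = 7.0 percentage points. If recurrence differs by 10 to 20 points between the levels (assumed), the unadjusted difference shifts by 0.070 × 10 = 0.7 to 0.070 × 20 = 1.4 points. The target is 9 points and the standard error 3.1. At the 30- and 40-point gaps in the last two table rows, the same arithmetic gives 2.1 and 2.8 points.

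**The case against.** The strongest reply is that nothing is wrong. An unadjusted chi-square in a randomised trial is valid, controls type I error, matches the sample-size calculation and exceeds the stated power. Its p-value already allows for chance imbalance. All of that stands.

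The second reply also stands: the gain is assumed. The Background calls obesity a risk factor for AF, but no section says how strongly baseline BMI, AF type or AF duration predicts recurrence after ablation. BMI is also restricted to 27 or more, which may weaken it as a predictor. With weak covariates the gain is at most 1 to 2 points.

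The reply that adjustment changes the question does not stand for the estimator proposed here. A conditional odds ratio would change it; a standardised risk difference targets the same marginal contrast as the 2×2 table. Nor is timing a real obstacle. BMI is an eligibility criterion, and AF type and duration are history items that treatment would not alter, although the documents do not say outright that they are recorded before randomisation.

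Three stronger readings are tempting, and the documents support none of them:
- *The primary test is biased or invalid.* It is neither.
- *The trial is underpowered without adjustment.* Potential Risks says around 5% cannot tolerate any dose. If those patients had control-level recurrence, the metformin rate would be 0.95 × 0.21 + 0.05 × 0.30 = 0.2145 and power about 78%. But the plan does not say whether its 30% reduction already allows for this.
- *A gain of 10 points is on offer.* The three-covariate simulation reached that only at AUC 0.81, for which the documents give no basis.

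**Conclusion.** The point holds as an efficiency improvement of uncertain size. The planned test is valid and has about 82% power at 388 per arm. Prespecified adjustment would add about 0 to 6 points: none if the covariates are not prognostic, about 1 at 20%/40% control recurrence by AF type, about 3 at 15%/45% and about 6 at 10%/50%. This rests on the plan's 30% v 21%, 3% attrition, an assumed even split of AF type and assumed prognostic strengths. The upper end has no documentary support; the lower end shows that adjustment costs essentially no power. Protection against chance imbalance is a modest further benefit. The change is worth making because the data are already to be collected, but leaving the plan as it is would not undermine the result.

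**What to change.** In the Statistics section, before any outcome data are seen, specify:
- **Primary analysis:** logistic regression of the primary sinus-rhythm outcome on randomised arm, baseline AF type, AF duration and baseline BMI.
- **Reported effect:** the standardised (marginal) risk difference with a 95% CI, using a variance method suited to that estimator, such as one based on its influence function.
- **Covariates:** AF-type categories and the coding of AF duration and BMI fixed in advance, since the protocol does not define the first two; simple imputation of any missing baseline value.
- **Supporting analysis:** the unadjusted Pearson chi-square.

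The model needs a single outcome definition. Trial Objective and Purpose refers to sinus rhythm after six months, whereas Outcomes and Assessment of Efficacy refers to 3 and 6 months, so that should be settled in the same revision.

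The cost is a little more analysis specification. No new data, visits or patients are needed, and the sample size stays at 400 per arm.

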### **Trial Objective and Purpose:**

The purpose of this trial is to determine if the upstream use of metformin in patients with atrial fibrillation and obesity undergoing a rhythm control strategy will increase the frequency of maintenance of sinus rhythm at six months. The primary endpoint is the number of patients in normal sinus rhythm after six months of follow up. Secondary endpoints are amount of weight loss, change in BMI, change in hemoglobin A1c, number of thromboembolic events, and burden of atrial fibrillation based on the Atrial Fibrillation Severity Score (AFSS).

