#### **Outcomes and Assessment of Efficacy:**

The primary outcome by intention to treat analysis will be maintenance of sinus rhythm by chart review, EKG, and Atrial Fibrillation Severity Score at 3 and 6 months after the initial attempt at rhythm control.

Secondary outcomes will include hospitalization related to arrhythmic events or medication side effects, number of antiarrhythmic medications, number of repeat ablations, BMI, Hemoglobin A1c, and number of thromboembolic events.

Pre-specified subgroup comparisons will include comparing patients randomized to metformin who have a 5% reduction in weight at 6 months to all control patients who achieve a 5% reduction in weight, and to all control patients.

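### Continuous secondary outcomes are planned as unadjusted ANOVA, with the response worded inconsistently, although the baselines needed for a more precise ANCOVA are already collected

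*Combined protocol and SAP*

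**What the plan says.** The Statistics section gives the whole plan for continuous outcomes in one sentence, "Analysis of Variance will be used for continuous variables", followed by the general rule "All tests are two-sided and P < .05 will be used to indicate a statistically significant difference". It names no covariate, response or visit. No other section adds an adjusted or repeated-measures model.

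The outcomes are worded differently in two places:

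- Trial Objective and Purpose: "Secondary endpoints are amount of weight loss, change in BMI, change in hemoglobin A1c". The same list adds AF burden from the AFSS, which is not worded as a change.
- Outcomes and Assessment of Efficacy: "number of repeat ablations, BMI, Hemoglobin A1c, and number of thromboembolic events". Here BMI and HbA1c carry no reference to change, weight is not in the list, and the AFSS forms part of the primary outcome.

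The baselines are planned for all patients. The list in Trial Design begins "Age, Gender, Weight, BMI, Tobacco Use, Hypertension, Hemoglobin A1c, Hyperlipidemia, serum CRP", and an AFSS survey is completed at the same time. Weight, BMI, HbA1c and AFSS are then repeated at the first rhythm-control attempt, at 3 months and at 6 months.

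**The concern.** Two things are left open that one sentence could settle.

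First, the response is undefined. An analyst could run ANOVA on 6-month BMI or on change in BMI and claim in either case to follow the plan. The two analyses differ in precision and can give different p-values.

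Second, neither version makes the best use of the baseline. ANOVA of the value ignores it. ANOVA of the change subtracts all of it, which over-corrects when the correlation is modest. ANCOVA estimates how much to subtract.

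At stake is the precision of the secondary comparisons. These matter to the trial's rationale, because weight loss is one of the two routes by which the background sections expect metformin to act.

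**Working it through.** **Plan's own figure.** The only sample size stated is for the binary primary outcome: "Using an 80% power at a 95% confidence interval", "We expect a 30% recurrence of AF after patients undergo ablation" and "we expect the recurrence of AF to be 30% less in the intervention group of patients on metformin than the control group". Reading the last as relative gives p₁ = 0.30 and p₂ = 0.30 × 0.70 = 0.21, with mean 0.255.

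- Without continuity correction: n = [1.960·√(2 × 0.255 × 0.745) + 0.842·√(0.30 × 0.70 + 0.21 × 0.79)]² / 0.09² = 367 per arm.
- With continuity correction: n′ = (n/4)·[1 + √(1 + 4/(0.09n))]² = 389 per arm.
- Allowing for 3% attrition: 389/0.97 = 402 after rounding up, against 400 stated.

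So the plan's figure reproduces, but it says nothing about continuous outcomes. The documents give no SD, correlation or power for any of those.

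**Inputs for the continuous outcomes.**

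- Evaluable per arm: 400 × 0.97 = 388 (Statistics).
- Two-sided alpha 0.05 (Statistics). The 80% power is borrowed from the primary calculation.
- Correlation r between baseline and 6-month value: an assumption, shown as a range.
- Equal SD σ at both times, and large-sample variances.

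**Formulas.** The variance of the treatment difference is (2σ²/n)·k, where

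- ANOVA of the 6-month value: k = 1
- ANOVA of change: k = 2(1−r)
- ANCOVA: k = 1−r²

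Therefore ANCOVA/change = (1−r²)/[2(1−r)] = (1+r)/2, and ANCOVA/value = 1−r². The difference detectable with 388 per arm, in units of σ, is (1.960 + 0.842)·√(2/388)·√k = 0.201·√k.

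| r | k, change | k, ANCOVA | ANCOVA/change | ANCOVA/value | Detectable difference (σ): value / change / ANCOVA |
|---|---|---|---|---|---|
| 0.3 | 1.40 | 0.91 | 0.65 | 0.91 | 0.201 / 0.238 / 0.192 |
| 0.5 | 1.00 | 0.75 | 0.75 | 0.75 | 0.201 / 0.201 / 0.174 |
| 0.7 | 0.60 | 0.51 | 0.85 | 0.51 | 0.201 / 0.156 / 0.144 |
| 0.9 | 0.20 | 0.19 | 0.95 | 0.19 | 0.201 / 0.090 / 0.088 |
| 0.95 | 0.10 | 0.0975 | 0.975 | 0.0975 | 0.201 / 0.064 / 0.063 |

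ANCOVA is at least as precise as either ANOVA in every row. This is general in large samples: value and change correspond to fixed slopes of 0 and 1 on the baseline, and ANCOVA uses the slope with the smallest variance.

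**Which column applies to which outcome.**

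- Weight: worded only as a loss, so only ANCOVA/change applies.
- BMI and HbA1c: ANCOVA/change under the Objective wording, ANCOVA/value under the Outcomes wording.
- AFSS: ANCOVA/value under the Objective wording. In the Outcomes section it belongs to the primary outcome instead.

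**The case against.** The case for leaving the plan alone has real substance. Under randomisation, unadjusted ANOVA is unbiased with correct type I error. The Statistics sentence is better read as under-specified than as a decision to ignore the baseline. The Objective section already words weight, BMI and HbA1c as changes, and weight and BMI over several months may well correlate at 0.9 or more, which leaves a variance gain of 5% or less. All these outcomes are secondary. All of this stands, and it makes the point small for weight. It does not remove the conflict between the two outcome sections. Nor does it cover AFSS or HbA1c, should their correlations be lower.

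Three stronger readings are tempting and are not supported.

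- *A reader might infer that the trial could well miss a weight effect.* With a 3.2 kg difference, an assumed SD of 20 kg and 388 per arm, comparing raw follow-up weights has about 61% power, against 96% for ANCOVA at r = 0.8. But no section plans a comparison of raw weights: the Outcomes list omits weight, the Objective speaks of loss, and the subgroup definition uses a percentage reduction. On change, the same assumptions give 94.1% against 96.0%. The 3.2 kg is an 18-month result from a cited trial in patients with coronary disease, not a planning value for this trial.
- *A reader might infer that chance baseline imbalance biases the result.* It does not. That variation is already in the standard error.
- *A reader might count CRP among the affected outcomes.* It is a scheduled measurement, but neither section lists it as an outcome.

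**Conclusion.** The point holds as a free improvement to the secondary analyses. The planned ANOVA is valid but leaves available precision unused, and the wording of the response is inconsistent.

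Against ANOVA of change, the variance reduction runs from 25% at r = 0.5 to 2.5% at r = 0.95. Against ANOVA of the 6-month value, the variance is about halved at r = 0.7, but only for BMI, HbA1c and AFSS under the wordings that give them as values. For weight loss analysed as a change, the gain is probably small.

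These sizes rest on assumed correlations, equal SDs at the two times and large-sample variances. The direction of the result does not depend on the value of r. The chi-square test of the primary outcome and the 400 per arm do not change.

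**What to change.** Replace the ANOVA sentence in the Statistics section with:

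> Weight, BMI, HbA1c and, where analysed as a continuous secondary outcome, AFSS at 6 months will be compared between arms by ANCOVA with treatment as factor and the baseline value of that outcome as covariate.

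The covariate should be the assessment made before study drug starts. The value at the first rhythm-control attempt will not serve, because by then the metformin arm is six weeks into treatment.

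Then align the two outcome sections: the same list in both, the same wording for BMI and HbA1c, weight either in both or in neither, and one stated role for AFSS. With the baseline as covariate, the estimated treatment effect is the same whether the response is the 6-month value or the change, so the choice between them no longer affects the result. CRP should not be added as an outcome through this edit.

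The cost is one sentence, matching edits to two lists and one degree of freedom per model. No new data, visits or patients are needed. The change should be made before outcome data are examined by arm.
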